6.11.2 Efficacy Analysis Methodology

6.11.2.1 Analysis of Primary Efficacy Variable

The primary comparison of progression-free survival between KW-0761 and vorinostat will be performed on the ITT set based upon the results of the on-site Investigator's assessment using a stratified Log-rank test at the one-sided 2.5% significance level. Stratification is done by disease type (MF or SS), disease stage (IB/II or III/ IV), and region (U.S., Japan, and Rest of World). A Cox proportional hazard model with treatment, disease type, disease stage, and region (U.S., Japan, and Rest of World) as covariates will be used to assess the magnitude of the treatment difference in PFS. The hazard ratio along with the 95% confidence interval obtained from the Cox proportional hazard model will be presented. Additional analyses may be performed adjusting for treatment and other baseline characteristics.

The median PFS and the 2-sided 95% confidence interval for each treatment will be estimated using the Kaplan-Meier survival analysis methods. Kaplan-Meier estimate of PFS rates and the corresponding 95% confidence interval will also be provided for each treatment arm by 6 months intervals. Plots of the Kaplan-Meier estimate of the survival distribution function over time for PFS will be presented by treatment arm.

The primary analysis of PFS will be performed when 255 total PFS events have been observed or 24 months after the last randomized subject's first dose, whichever comes first.

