Appropriate contrasts will be used to determine the difference between the Vorinostat treatment group and the KW-0761 treatment group across the end of Cycles 1, 3, and 5. In case of convergence problems, another variance-covariance structure will be considered. The selection of any of these structures will be determined after exploration of the observed correlation structure. Least squares (LS) means, corresponding standard errors, 95% two-sided confidence intervals will be presented for the within-group change for odd cycles. For the between-treatment group comparison, the difference in LS means, corresponding standard errors, 95% two-sided confidence intervals, and two-sided p-value will also be derived from this ANCOVA model and presented for the odd cycles. This mixed-effects model will also be used to compare the treatment differences in the mean changes in Skindex-29 score from baseline to each scheduled time point at end of cycle 1, cycle 3, and cycle 5. In addition to

the Skindex-29 score, a Skindex score based on a subset of Skindex questions may be analyzed in a similar fashion.¹¹

Standard model diagnostics will be performed to assess the validity of the proposed ANCOVA model. These diagnostics will include an examination of the residuals for normality and homoscedasticity as well as testing for the significance of the treatment by baseline interaction term. If the residuals are not normally distributed, then the analysis will be carried out using Wilcoxon rank sum test instead.

In addition to the analysis described above, summary statistics including n, mean, standard deviation, median, minimum, and maximum will be provided for Skindex-29 score at baseline and each scheduled time point and change in total score at each of these scheduled assessments for each treatment arm.

The same methods described above for the analysis of change in Skindex-29 score will be performed for the analysis of change from baseline for the ends of cycle 1,3, and 5 in FACT-G total score and EQ-5D-3L index score.

Comparisons of these four key secondary endpoints between the two treatment arms will be conducted using p-values that are adjusted to control the overall study-wise Type 1 error rate to be less than 0.05. The four statistical tests that will be conducted are:

- ORR as assessed by the Investigator,
- Change in Skindex-29 score at through the 6-month assessment,
- Change in FACT-G total score at through the 6-month assessment, and

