- Change in EQ-5D-3L index score at through the 6-month assessment.

Since these tests are not independent, the four key secondary tests will be conducted using the Sidak adjusted p-value method defined as:

Adjusted p-value = $1-(1-p)^4$ where **p** is the original p-value of the individual test.

These adjusted p-values will then be compared to .05 for each test.

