Rate (%) of Being Alive without Progression for at Least***		
6 months (95% CI)	xx.x (xx.x, xx.x)	xx.x (xx.x, xx.x)
12 months (95% CI)	xx.x (xx.x, xx.x)	xx.x (xx.x, xx.x)
18 months (95% CI)	xx.x (xx.x, xx.x)	xx.x (xx.x, xx.x)
24 months (95% CI)	xx.x (xx.x, xx.x)	xx.x (xx.x, xx.x)
Etc.		

Note: Percentage is calculated using the number of subjects in the column heading as the denominator.

* 95% CIs are obtained from SAS proc lifetest using loglog transformation.

** Hazard ratio and 95% CI are based on Cox proportional hazards model with treatment, disease type, disease stage, and region as covariates. P-value (two-sided) is obtained from a stratified log rank test (one-sided test at 0.025 level or equivalently two-sided test at 0.05 level) with disease type, disease stage, and region as stratification factors.

*** Kaplan-Meier estimate.

The following tables will have similar layout as Table 14.2.1.1:

Table 14.2.1.2
Summary of Progression-Free Survival (PFS) Based on Investigator's Assessment
Sensitivity Analysis 1
Intent-to-Treat Set

Table 14.2.1.3
Summary of Progression-Free Survival (PFS) Based on Investigator's Assessment
Sensitivity Analysis 2
Intent-to-Treat Set

Table 14.2.1.4
Summary of Progression-Free Survival (PFS) Based on Investigator's Assessment - Worst Case Sensitivity Analysis
Sensitivity Analysis 3
Intent-to-Treat Set

<<Programming Note: Add the corresponding PFS definition in the footnote for Tables 14.2.1.2 to 14.2.1.4 per SAP Section 6.11.2.2.>>

Table 14.2.1.5
 Multivariate Analysis of Progression-Free Survival (PFS) Based on Investigator's Assessment
 Intent-to-Treat Set

Prognostic Factors	----- Progression-Free Survival (Months) -----	
	Hazard Ratio (95% CI)	P-value
Treatment		
KW-0761 vs. Vorinostat	xx.x (xx.x, xx.x)	x.xxxx
Disease Type		
MF vs. SS	xx.x (xx.x, xx.x)	x.xxxx
Disease Stage		
IB/II vs. III/IV	xx.x (xx.x, xx.x)	x.xxxx
Blood Involvement		
Yes vs. No	xx.x (xx.x, xx.x)	x.xxxx
Region		
US vs. Japan	xx.x (xx.x, xx.x)	x.xxxx
US vs. Rest of World	xx.x (xx.x, xx.x)	x.xxxx
Japan vs Rest of World	xx.x (xx.x, xx.x)	x.xxxx
Age Group		
>=65 vs. <65 yrs	xx.x (xx.x, xx.x)	x.xxxx
Gender		
Male vs. female	xx.x (xx.x, xx.x)	x.xxxx
Race Category		
White vs. Black or African American	xx.x (xx.x, xx.x)	x.xxxx
White vs. Other	xx.x (xx.x, xx.x)	x.xxxx

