12 months (95% CI)	xx.x (xx.x, xx.x)	xx.x (xx.x, xx.x)
18 months (95% CI)	xx.x (xx.x, xx.x)	xx.x (xx.x, xx.x)
24 months (95% CI)	xx.x (xx.x, xx.x)	xx.x (xx.x, xx.x)
Etc.		

Note: Percentage is calculated using the number of subjects in the column heading as the denominator.

* 95% CIs are obtained from SAS proc lifetest using loglog transformation.

** Hazard ratio and 95% CI are based on Cox proportional hazards model with treatment, disease type, disease stage, and region as covariates. P-value (two-sided) is obtained from a stratified log rank test (one-sided test at 0.025 level or equivalently two-sided test at 0.05 level) with disease type disease stage, and region as stratification factors.

*** Kaplan-Meier estimate.

Table 14.2.2.1.1
 Summary of Confirmed Overall Response Rate (ORR) During Randomized Treatment Period
 Intent-to-Treat Set

	Vorinostat N=xxx	KW-0761 N=xxx
By Investigator's Assessment		
Overall response rate (confirmed CR + PR) (n, %)	xx (xx.x)	xx (xx.x)
95% CI*	(xx.x, xx.x)	(xx.x, xx.x)
----- Treatment Comparison -----		
KW-0761 vs. Vorinostat		
Risk Diff		xx.x
95% CI*		(xx.x, xx.x)
P-value**		x.xxxx
Adjusted P-value**		x.xxxx
By Independent Review Committee		
Overall response rate (confirmed CR + PR) (n, %)	xx (xx.x)	xx (xx.x)
95% CI*	(xx.x, xx.x)	(xx.x, xx.x)
----- Treatment Comparison -----		
KW-0761 vs. Vorinostat		
Risk Diff	xx.x	xx.x
95% CI*	(xx.x, xx.x)	(xx.x, xx.x)
P-value**		x.xxxx

Note: Percentage is calculated using the number of subjects in the column heading as the denominator. CR = complete response, PR = partial response.

Overall Response Rate is based on Global Composite Response Score.

* 95% CI for response rate is the exact 95% confidence interval. 95% CI for difference is the exact 95% unconditional confidence interval for the risk difference (KW-0761 - Vorinostat).

**P-value is obtained from Cochran-Mantel-Haenszel test adjusting for disease type, disease stage, and region. Adjusted P-value is calculated using Sidak method.

Table 14.2.2.1.2
 Logistic Regression Analysis of Confirmed Overall Response Rate (ORR) During Randomized Treatment Period
 Based on Investigator's Assessment
 Intent-to-Treat Set

Prognostic Factor	Odds Ratio Estimate (SE)	95% CI	P-value
Treatment			
KW-0761 vs. Vorinostat	xx.x (xx.xx)	(xx.x, xx.x)	x.xxxx
Disease Type			
MF vs. SS	xx.x (xx.xx)	(xx.x, xx.x)	x.xxxx
Disease Stage			
IB/II vs. III/IV	xx.x (xx.xx)	(xx.x, xx.x)	x.xxxx
Blood Involvement			

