Note: LS mean, SE, 95% CI and P-value are from MMRM with treatment, disease stage, and region as fixed effects and baseline score as a covariate. Adjusted P-value is calculated using Sidak method for the overall difference across time points through 6-month assessment (including End of Cycles 1, 3, and 5 timepoints only). Time points beyond Cycle 11 are not included due to the small number of subjects on study after cycle 11.

<<Programming Note: Repeat for Symptoms Scale Score, Emotions Scale Score, and Functioning Scale Score. Adjusted p-value is only presented for the overall treatment difference through 6-month assessment for the Skindex-29 score including the End of Cycle 1, End of Cycle 3, and End of Cycle 5 time points.>>

The following tables will have similar layout as Table 14.2.3.1 and Table 14.2.3.2:

Table 14.2.3.3
Summary of Skindex-29 Score and Change from Baseline by Visit During Randomized Treatment Period
Efficacy Evaluable Set

Table 14.2.3.4
Analysis of Change in Skindex-29 Score from Baseline During Randomized Treatment Period
Efficacy Evaluable Set

Table 14.2.3.5
Summary of Skindex-29 Score and Change from Baseline by Visit During Crossover Portion
Intent-to-Treat Set
Subjects Who Are Randomized to Vorinostat and Crossed Over to KW-0761

<<Programming Note: For tables 14.2.3.3 and 14.2.3.5, all scheduled timepoints according to the study procedures will be presented. >>

The following tables will have similar layout as Table 14.2.3.1 and Table 14.2.3.2:

Table 14.2.4.1
Summary of FACT-G Total Score and Change from Baseline by Visit During Randomized Treatment Period
Intent-to-Treat Set

Table 14.2.4.2
Analysis of Change in FACT-G Total Score from Baseline During Randomized Treatment Period
Intent-to-Treat Set

Table 14.2.4.3
Summary of FACT-G Total Score and Change from Baseline by Visit During Randomized Treatment Period
Efficacy Evaluable Set

Table 14.2.4.4
Analysis of Change in FACT-G Total Score from Baseline During Randomized Treatment Period
Efficacy Evaluable Set

Table 14.2.4.5
Summary of FACT-G Total Score and Change from Baseline by Visit During Crossover Portion
Intent-to-Treat Set
Subjects Who Are Randomized to Vorinostat and Crossed Over to KW-0761

Table 14.2.4.6
Summary of FACT-G Physical Well-Being Score and Change from Baseline by Visit During Randomized Treatment Period
Intent-to-Treat Set

Table 14.2.4.7
Summary of FACT-G Social Well-Being Score and Change from Baseline by Visit During Randomized Treatment Period

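### The Sidak adjustment covers only the four key secondary endpoints and nothing gates them on PFS, so the claimed study-wise Type 1 error below 0.05 is not guaranteed

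*SAP*

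**What the plan says.** The primary comparison of PFS is made "using a stratified Log-rank test at the one-sided 2.5% significance level" (SAP 6.11.2.1). The footnote to mock Table 14.2.1.1 describes this as a "one-sided test at 0.025 level or equivalently two-sided test at 0.05 level".

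SAP 6.11.2.3 then names four key secondary comparisons: investigator-assessed ORR and the changes in Skindex-29, FACT-G and EQ-5D-3L through six months. Their p-values are to be "adjusted to control the overall study-wise Type 1 error rate to be less than 0.05". Each raw p is converted to 1 − (1 − p)^4, and the rule ends: "These adjusted p-values will then be compared to .05 for each test". Protocol 10.3 gives the same rule and the same aim. For the quality-of-life endpoints the "two-sided p-value will also be derived from this ANCOVA model".

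No section of either document says that the secondary tests are performed, or interpreted as confirmatory, only if PFS is significant. The mock tables have no such condition either. The ORR footnote (Table 14.2.2.1.1) reads "Adjusted P-value is calculated using Sidak method" and the Skindex-29 footnote (Table 14.2.3.2) reads "Adjusted P-value is calculated using Sidak method for the overall difference across time points".

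**The concern.** The stated aim concerns the whole study, but the device covers part of it. An exponent of 4 accounts for four tests. The fifth confirmatory test, PFS, has its own separate allocation. Two families, each tested at its full level with no order between them, do not share one 0.05 error rate.

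Naming the endpoints primary and key secondary does not by itself create a testing order. If KW-0761 does not truly improve PFS, the plan as written still lets an ORR or quality-of-life result be declared significant under a study-wise label. The trial is open-label, ORR is investigator-assessed and the quality-of-life scores are self-reported, so the conditions for a claim on these endpoints should be fixed in writing.

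**Working it through.** **Inputs from the documents**
- PFS: one-sided 0.025 (SAP 6.11.2.1), critical value z = 1.960.
- Key secondaries: four, adjusted p = 1 − (1 − p)^4 compared with 0.05 (SAP 6.11.2.3).
- Quality-of-life tests: two-sided (SAP 6.11.2.3).
- No interim analysis (SAP 6.5), so no other alpha is spent.

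**Assumptions**
- ORR is tested two-sided. The text does not say so, but the plain CMH call in SAP 8.2.5 gives a non-directional statistic.
- The five test statistics are jointly normal with a common correlation ρ. The documents say only that the tests are not independent, so ρ is shown over a range.

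**Step 1: the secondary family alone.** The adjusted p is below 0.05 when the raw p is below 1 − 0.95^(1/4) = 0.01274, that is |z| > 2.491. With four independent tests the family error is 1 − (1 − 0.01274)^4 = 0.0500. At ρ = 0.3, 0.5 and 0.7 it is 0.048, 0.044 and 0.037. Exponent 4 therefore does what it should for this family.

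**Step 2: add PFS, no gate, all nulls true.** Under independence:

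1 − (1 − 0.025) × (1 − 0.0500) = 1 − 0.975 × 0.95 = 0.0738.

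On the two-sided reading of PFS in the Table 14.2.1.1 footnote: 1 − 0.95 × 0.95 = 0.0975.

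Counting only false claims favouring KW-0761, each secondary contributes 0.01274/2 = 0.00637: 1 − 0.975 × (1 − 0.00637)^4 = 0.0496.

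**Step 3: correlation** (numerical integration over the shared normal component)

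| ρ | PFS one-sided, secondaries two-sided | PFS two-sided, secondaries two-sided | Claims for KW-0761 only |
|---|---|---|---|
| 0 | 0.074 | 0.098 | 0.050 |
| 0.3 | 0.070 | 0.092 | 0.046 |
| 0.5 | 0.064 | 0.084 | 0.042 |
| 0.7 | 0.054 | 0.071 | 0.036 |
| 0.9 | 0.041 | 0.055 | 0.028 |

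The first column crosses 0.05 at ρ of about 0.77 and is 0.048 at 0.8. The second is above 0.05 at every value shown.

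**Step 4: with a PFS gate.** If PFS is null, no secondary claim is possible without a PFS error first, so the study-wise error is 0.025 (0.05 if PFS is counted two-sided). If PFS is truly effective at the planned power (about 90%) and all four secondaries are null, the error is 0.90 × 0.050 = 0.045 at ρ = 0 and falls to 0.023 at ρ = 0.7.

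**Step 5: the alternative of one Sidak family of five.** The per-test level becomes 1 − 0.95^(1/5) = 0.01021 two-sided. With a hazard ratio of 169/254 = 0.665 and 255 events (Schoenfeld), PFS power falls from 90.2% to 75.3%; restoring 90% needs about 358 events.

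**The case against.** The strongest reply is directional. The errors that matter most are false claims for KW-0761, and on that count the plan stays just under 0.05 even at independence (0.0496). The 0.074 goes above 0.05 only because it includes false secondary findings in favour of vorinostat. The arithmetic is right and should be reported beside the headline figure. It does not rescue the stated property. The quality-of-life p-values are explicitly two-sided, so a directional count is not the scale the plan uses. On a directional scale, the level matching the PFS test is 0.025, and 0.0496 is about twice that.

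A second reply is that the size depends on convention and on an unknown correlation. It does, which is why the figures are given as a range. The one-sided PFS count used for the headline is milder than the SAP's own two-sided equivalent, and a guarantee cannot rest on an unstated correlation of 0.77 or more.

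Third, the practical reach is narrow: there is excess error only if PFS is truly null, and no text says a secondary result can rescue a failed primary. This limits the consequence. But no text rules it out either, and an unwritten convention is not pre-specification.

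Two smaller points stand. Sidak is exact for independent tests and conservative for jointly normal two-sided ones; under arbitrary dependence the family bound is 4 × 0.01274 = 0.051, a trivial excess. This also means that citing non-independence as the reason for choosing Sidak is the wrong way round. And timing matters: the SAP is dated 22 November 2016 and says it was finalised before database lock, while the supplied protocol already refers to Amendment 10. The documents give no lock date.

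**Conclusion.** The concern holds. The plan claims study-wise control below 0.05 but delivers control only within the four-endpoint secondary family (0.050). With all nulls true, the ungated error is 0.074 at independence and 0.054 at a common correlation of 0.7, counting PFS one-sided and the secondaries two-sided. It is up to 0.098 if PFS is counted two-sided, and 0.050 or less if only claims for KW-0761 are counted. These figures assume jointly normal statistics with a common correlation and a two-sided ORR test.

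If PFS is truly improved, the secondary-family error stays at or below 0.05 under the same normality assumption. The primary test, its alpha and the 255 events are not touched. This should be fixed, but it does not threaten the primary analysis.

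**What to change.** Add to SAP 6.11.2.3 and Protocol 10.3: *The four key secondary endpoints will be formally tested only if the primary PFS test is significant at one-sided 0.025; otherwise their p-values are descriptive.* Keep Sidak with exponent 4 inside the gate, and repeat the condition in the footnotes of the mock tables that print adjusted p-values. Study-wise error is then at most 0.05 for jointly normal statistics.

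The cost is one sentence per document plus the footnotes, made before database lock, with no change to PFS alpha, events or data collection. The price is that no confirmatory secondary claim is possible if PFS fails. Extending Sidak to all five tests is not recommended because of the loss of PFS power.

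If the sponsor does not want a gate, or the database is already locked so that a gate would be post hoc, limit the claim to control within the family of four key secondary endpoints and drop the reference to the study as a whole. That costs nothing except the study-wise claim.

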The duration of response (DOR), which will be estimated using survival analysis methods, is measured from the time measurement criteria are met for CR/PR (whichever is first recorded) until the first date that PD or death is objectively documented (taking as a reference for PD that smallest measurement recorded since the treatment started). Subjects who do not relapse will be censored at the day of their last tumor assessment. The DOR will be estimated separately for each treatment arm. Because the DOR is a conditional estimate (conditional on having a response), comparison between KW-0761 and vorinostat would not be based on randomized groups and therefore will not be made.

The Pruritus Evaluation (Likert scale & Itchy QoL) and Skindex-29, FACT-G and EQ-5D-3L assessments will be summarized at baseline and at the timepoints specified in the study procedures tables for each arm. The improvement (change from baseline) for each of these measures will also be summarized and analyzed using repeated measures ANCOVA utilizing time points through the 6-month assessment.

For those subjects who crossover from the vorinostat arm to the KW-0761 arm, these assessments within the second arm of the study will be measured at the end of the first cycle after the first day of dosing for KW-0761. Baseline measurements for crossover subjects are those documented closest to and before the first KW-0761 infusion. No statistical comparisons will be made for information gathered in the crossover from the vorinostat arm to the KW-0761 arm. All summaries for this arm will be purely descriptive.

Progression-free survival is the primary endpoint in this study. There are four key secondary endpoints in this study that require a comparison between treatment arms: ORR, Skindex-29, FACT-G, and EQ-5D-3L. Comparisons of these four secondary endpoints between the 2 treatment arms will be conducted using p-values that are adjusted to control the overall study-wise Type 1 error rate to be less than 0.05. Since these tests are not independent, the four secondary tests will be conducted using the Sidak adjusted p-value method defined as **Adjusted p-value = $1-(1-p)^4$** where **p** is the original p-value of the individual test

These adjusted p-values will then be compared to .05 for each test.

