6.11.2.3 Analyses of Key Secondary Efficacy Variables

There are four key secondary endpoints in this study that require a comparison between treatment arms: ORR as assessed by the Investigator, changes in Skindex-29 score, FACT-G total score, and EQ-5D-3L index score. All assessments up to 6-months will be of interest for this analysis.

ORR as assessed by the Investigator will be compared between the 2 treatment arms using Cochran-Mantel-Haenszel (CMH) test adjusted for disease type, disease stage, and region. Additional analyses may be performed adjusting for treatment and other baseline characteristics. The exact 95% confidence intervals for ORR will be calculated for each treatment arm along with the difference in response rates between the two treatment arms. All 95% confidence intervals on individual rates will be computed using exact computational methods. Any confidence interval on the difference of proportions will be computed using exact unconditional confidence limits for the risk difference. These confidence intervals can be constructed using SAS[®] version 9.3 with the FREQ procedure specifying the RISKDIFF option in the EXACT statement.¹⁰ In addition to the results described above, the number and percentage of subjects achieving objective response (CR or PR) will be presented for each treatment arm.

The treatment differences in the mean change of Skindex-29 score from baseline across each planned timepoint (end of cycle 1, cycle 3, cycle 5) up to 6 months of assessments will be tested using a repeated measures mixed effects model with time, region, disease type, disease stage, treatment, and time-by-treatment interaction as factors and baseline score as a covariate. Restricted Maximum Likelihood (REML) method will be used. An unstructured covariance matrix will be employed to model the correlation among repeated measurements.

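### The four key secondary tests use single-step Sidak, justified by dependence; the rule is valid, but step-down Sidak keeps the same 0.05 family bound and never rejects fewer hypotheses

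*SAP*

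**What the plan says.** SAP section 6.11.2.3 sets up the family: "There are four key secondary endpoints in this study that require a comparison between treatment arms". They are ORR by the investigator and the changes in Skindex-29, FACT-G total and EQ-5D-3L index through the 6-month assessment. The p-values are to be "adjusted to control the overall study-wise Type 1 error rate to be less than 0.05". The method and its reason come in one sentence: "Since these tests are not independent, the four key secondary tests will be conducted using the Sidak adjusted p-value method". The formula raises (1-p) to the fourth power whatever the rank of the p-value, and then: "These adjusted p-values will then be compared to .05 for each test".

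Protocol section 10.3 gives the same formula and the same reason: "the four secondary tests will be conducted using the Sidak adjusted p-value method".

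Neither document describes an ordering, a step-down or a hierarchy among the four. Neither makes them conditional on a significant PFS result. No effect size, SD, response rate, correlation or power is given for any of the four. The planned confidence intervals for ORR and for the least-squares mean differences are ordinary 95% intervals.

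**The concern.** Two things look wrong. First, the reason does not fit the method. The expression 1-(1-p)^4 is the exact familywise adjustment when four tests are independent. Under dependence it stays valid for two-sided, jointly normal statistics through the Sidak inequality, but it becomes conservative. Dependence is something the rule tolerates, not a ground for choosing it.

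Second, a fixed exponent of 4 charges every test for all four hypotheses, even after some have been rejected. A step-down version uses the same inequality and charges each later test only for the hypotheses still open. What is at stake is power on the second, third and fourth endpoints, not the validity of the family.

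**Working it through.** **Inputs from the documents.** Four tests; p_adj = 1-(1-p)^4; comparison with 0.05; two-sided p-values for the QoL models (SAP 6.11.2.3). PFS is tested at one-sided 2.5%, which the shell of SAP Table 14.2.1.1 equates with two-sided 0.05.

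**The plan's own figure.** Solving 1-(1-p)^4 = 0.05 gives p = 1-0.95^(1/4) = 0.01274. Under independence the familywise error is 1-(1-0.01274)^4 = 0.0500, so the plan's 0.05 is reproduced. For four equally correlated normal statistics with all nulls true (300,000 simulated draws), it is 0.047 at correlation 0.3, 0.044 at 0.5 and 0.032 at 0.8. The rule holds and is conservative under positive correlation.

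**Step-down levels.** For the ordered p-values the raw levels are 1-0.95^(1/k) with k = 4, 3, 2, 1: 0.01274, 0.01695, 0.02532 and 0.05000. The first equals the single-step level and the rest are higher, so anything single-step rejects is rejected here too. Because the first level is the same, the chance of at least one rejection is the same. Simulated familywise error stayed at or below 0.05 in every setting tried (correlation -0.3 to 0.8, none to three real effects).

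**Power, by assumption only.** Each real effect has 80% power at unadjusted two-sided 0.05 and the correlation is 0.3:

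| Real effects | Mean power per real endpoint, single-step | Step-down | All real effects significant, single-step | Step-down |
|---|---|---|---|---|
| 1 | 62.2% | 62.3% | 62.2% | 62.3% |
| 2 | 62.2% | 64.5% | 43.2% | 47.7% |
| 3 | 62.2% | 67.5% | 31.9% | 43.2% |
| 4 | 62.2% | 71.7% | 24.8% | 47.0% |

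Over correlations 0 to 0.7 with four real effects, step-down mean power is 73% to 70% against 62%. At 90% unadjusted power and correlation 0.3, single-step gives 77%, and step-down gives 77%, 80%, 82% and 86% with one to four real effects.

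**Actual error when some effects are real.** With three real effects at 80% power and correlation 0.3, the chance of falsely rejecting the fourth rises from 1.3% to 3.3%. With three very strong effects it rises from 1.3% to about 4.6%. Both stay within 0.05.

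**Study-wise error without a gate.** Taking PFS at two-sided 0.05 and treating it as independent of the family, error over PFS plus the four tests can reach 1-0.95×0.95 = 0.0975 under either rule. If PFS is null, three secondaries are strongly positive and one is null, it is 1-0.95×(1-0.01274) = 0.062 for single-step and 0.0975 for step-down.

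**The case against.** The strongest defence is that nothing is broken. The rule is valid within the family, the protocol and SAP agree on it, and deleting the dependence clause alone changes no decision. That stands: this is an efficiency point, not an error in familywise control.

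It is also fair that step-down is not costless in every sense. The bound is the same, but the actual chance of a false secondary claim moves towards it when some effects are real, and that is where the power comes from. It is legitimate within the family, but it does nothing for the study-wise aim. Each adjusted p-value would also need all four raw p-values, whereas the shells now compute each from its own. The usual price of step-down, losing simple matching simultaneous intervals, does not apply because the SAP plans only unadjusted ones.

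A reader might infer that single-step markedly reduces power for all four endpoints. The documents do not support that. They give no basis for assuming that all four effects are real, and the gain is about nil with one real effect and about 2 points with two.

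**Conclusion.** The point holds as a minor improvement. Single-step Sidak is valid for the four tests, its stated reason is wrong, and step-down Sidak has the same 0.05 family bound and is never less powerful. The gain per real endpoint is about 0, 2, 5 or 10 points with one, two, three or four real effects. This assumes equally correlated normal statistics, correlation 0.3 and 80% unadjusted power for each real effect. The chance of winning at least one endpoint does not rise.

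A reader might also infer that either Sidak rule delivers the study-wise error below 0.05 that the SAP states as its aim. Neither does alone, because no text makes these tests conditional on PFS. That gap is separate and remains whichever rule is used.

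**What to change.** In SAP 6.11.2.3:

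- Replace the formula: order the p-values p(1) ≤ … ≤ p(4), set adjusted p(j) = max over i ≤ j of 1-(1-p(i))^(5-i), and compare each with 0.05.
- Delete the clause that gives dependence as the reason. This is worth doing even if single-step is kept.
- Identify the change as a departure from protocol section 10.3, as the SAP's introduction requires for substantial differences, and align the protocol if it is amended.
- Remove the Sidak-adjusted p-value from Table 14.2.2.1.4 (ORR by disease type). No QoL tests are planned within disease type, so there is no four-test family there to order.
- Update the footnotes of the ORR and QoL shells to say that the adjusted values use all four p-values.

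The cost is a short SAP edit and some programming, with no extra alpha, patients or visits and no planned interval lost. The accepted downside is the higher actual error, still within the 0.05 bound. The edit should be made before database lock and before any secondary comparison by arm is seen. A sentence testing the four only after a significant PFS result would be needed separately to meet the study-wise aim.
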